## 8.0 Potential Difficulties and Limitations

**8.1 Potential Difficulties.** Our intervention involves human subjects and technologies, which may result in a number of potential difficulties. Study results may be affected by adherence among participants. However, preliminary study by our lab suggested that most participants will be compliant and one of the feasibility outcome is adherence. Technology issues may arise throughout the intervention. Technology issues may include, but not limited to, the Wii Fit meter or Digit-Walker malfunctioning or the Wii Fit meter syncing issue, or issues with the Wii U or Xbox 360 consoles. To address possible technology issues, the facilitator and the project staff will be available to help participant problem solve technology issues at the weekly session or will be available by phone. Participants will be urged to contact the research staff if problems arise and defective monitors will be replaced.

**8.2 Limitations.** The Pink Warrior intervention does involve a more extensive facilitator training than the current support group format. Therefore, time for facilitator training may be an issue for future implementations. However, if the study proves feasible, then subsequent study will be conducted to evaluate how to efficiently deliver facilitator training. In addition, this study is also limited to the greater Galveston, TX community. Even though our pilot results may not be nationally generalizable, we will use our results to inform the design of a larger and generalizable study.

## **9.0 Ethics and Protection of Human Subjects**

Potential participants will be provided with an in-depth informed consent information prior to baseline assessments, being randomized, and beginning of study participation. The principal investigator (PI) or research staff will outline pertinent information and go over the consent form with each individual. All study personnel will be trained in the conduct of human research and only individuals authorized by the PI will have access to data on a need to know basis.

Extensive discussion of risks and possible benefits of participation will be provided to the potential participant. Consent forms describing in details the study procedures and risks will be IRB-approved and the potential participant will be asked to read and review the document. Upon reviewing the document, the investigator or staff will explain the research study to the potential participant and answer any questions that may arise. Potential participant will then sign the informed consent document prior to any study procedures. The potential participants will also have the opportunity to think about it prior to agreeing to participate.

Participants may withdraw consent at any time throughout the course of the trial. A copy of the informed consent document will be given to the participant for their records. The rights and welfare of the participants will be protected by emphasizing to them that the quality of their medical care will not be adversely affected if they decline to participate in this study.

We anticipate this study to present minimal risk depending on the age of the participant. Risks include breaches of confidentiality and acute musculoskeletal injuries (muscle soreness, sprains, skin irritation, sunburn). We have sought to minimize the risk by obtaining approval from their treating oncologist prior to participation. If participants follow the activity recommended by the program there should be no unintended consequences, but serious injuries may arise as a result of vigorous physical activity. In this event, the necessary actions defined by the IRB will be taken.

The design of this randomized controlled trial to include the control group is to assist the research team compare the different interventions. Participants in the control group still

receives a standard intervention with a basic pedometer. Despite randomization, participants in the control group will be offered the participant manual at the end of the intervention.

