	Prompting self-monitoring	Wii fit meter, weekly log (Cohorts 1 to 3) Wearable fitness tracker (Cohort 4)	Pedometer (Cohort 1 to 3) Wearable fitness tracker (Cohort 4)
	Barrier identification	Group session	
	Action planning	Weekly log, home-based worksheet, and group session	
Motivation			
Autonomy support	Provide information and provide choice	Non-directive group discussion, Group game play, ACS personal health manager kit	ACS personal health manager kit (general information)
Competence support	Feedback on performance	Badges, unlocking the game, weekly progress chart based on the Wii fit meter, other participants in the group, and from the facilitator	Pedometer
Relatedness	Social support	Group play, group session, and identification with other survivors	Identification with other survivors
	Social support—Emotional support	Group sessions on survivorship issues	Group sessions on survivorship issues
	Social support—Appraisal support	See the “friends” progress in the group	

**4.2 Participant Recruitment.** Participants will be recruited from Galveston county and surrounding counties, the University of Texas, Medical Branch (UTMB) clinics, UTMB-associated cancer care facilities, MD Anderson clinics and from cancer or volunteer registries. Recruitment of MD Anderson patients will occur in person at MD Anderson and joint MD Anderson/UTMB clinics as well as by phone & email (following the same procedures used to identify UTMB patients to approach. Due to the possible difficulty of recruitment, we have collaborated with oncologists. The oncologists will be referring their patients. The team will not approach patients until they provided the permission for the team to approach. For the other oncologists not on our protocol, a flyer will be provided to them for referral. Participants will contact the researchers if interested in participating. MD Anderson personnel ([name]) will be involved in recruitment activities for the fourth cohort (Note: UTMB and MD Anderson have entered into an agreement such that the clinical site is a collaborative single site operation by both institutions.)

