A recruitment letter will be mailed to contact potential participants in the cancer or volunteer registries. We will also collaborate with local cancer support groups. Newspaper advertisement and flyers will also be used as additional recruitment tools. We will recruit participants in three cohorts. First and second cohort will consist of 10 people, 5 in the intervention group and 5 in the control group. The third cohort will consist of 40 people, 20 in the intervention group and 20 in the control group. In order to randomize a total of 60 participants, we will need to recruit up to 80 individuals due to drop-outs between screening and randomization. The fourth cohort will consist of 20 people (age 55 and 79 to grant

restrictions), 10 in the intervention group and 10 in the control group. In order to randomize a total of 20 participants, we will need to recruit an additional 80 individuals to account for potential drop-outs between screening and randomization. A total of 160 individuals will be recruited for Cohort 1-4 in order to randomize a total of 80 participants. Screening script, recruitment letter, flyer, presentation blurb are presented in **Appendix A**.

4.3 Inclusion/Exclusion Criteria. Research staff will follow the screening script to determine eligibility when potential participants express interest in the study. Potential participants must meet all of the inclusion criteria in order to be eligible to participate in the study.

Primary inclusion criteria will include for Cohort 1-3:

- Provide informed consent
- Diagnosed with primary female breast cancer
- English-speaking between the ages of 18 years or older
- Able to read and write in English
- Obtained approval from oncologists for the participant to be involved in the physical activity based support group
- Able to travel to the UTMB sites (Victory Lakes or Galveston)
- Able to move arms and legs as well as ambulate
- Able to see TV screen from a distance of 2 to 4 feet

Primary inclusion criteria for Cohort 4 due to grant restrictions will include:

- Ability to provide informed consent
- Diagnosed with primary female breast cancer
- 55 years to 79
- Able to speak, read, and write in English
- Able to travel to UTMB locations and/or MD Anderson Victory Lakes
- Able to move arms and legs as well as ambulate
- Has a smartphone, tablet or computer and daily access to a reliable internet

Inclusion criteria for Cohort 4 due to pandemic (e.g., COVID-19) restrictions will include:

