- Ability to provide informed consent via telephone or through internet
- Diagnosed with primary female breast cancer
- 55 years to 79
- Able to speak, read, and write in English
- Able to move arms and legs as well as ambulate
- Has a smartphone, tablet or computer and daily access to a reliable internet

Potential participant meeting any of the exclusion criteria at screening will be excluded from study participation

Ineligibility criteria will include:

- Being pregnant
- Dementia
- Currently engage in  $\geq 150$  minutes of planned moderate physical activity per week for the prior week

- Are involved in another physical activity intervention

Ineligibility criteria for Cohort 4 will include all criteria listed above. However, cohort 4 has an addition of no access to an internet-connected smart device (smartphone, tablet, or computer) being an ineligibility criterion.

**4.3 Randomization Procedures.** Participant in cohorts 1 to 3 will be randomly assigned to be in the active video game-based physical activity intervention group (intervention group) or the existing UTMB Breast Cancer support group with pedometer (control group). Participant in cohort 4 will be randomly assigned to be in the weekly active video game web-based group sessions with wearable tracker (intervention group) or receive weekly conference calls plus wearable tracker (control group). We will randomize participants by using sequentially numbered opaque sealed envelopes for cohorts 1 to 4. The sequentially number will be the Study ID #1 to #80 for cohort 1-3. A project staff who is not involved in the assessment will use the random number generator (<https://www.randomizer.org/>) to assign each study ID number to either intervention group or control group. The project staff who is not involved in the assessment will write the group assignments will be written on pieces of paper, placed under a piece of carbon paper, wrapped in aluminum foil, and then sealed one per opaque envelope. The same procedure will be used for cohort 4.

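### The ethics section names treating-oncologist approval as a safeguard for the whole study, but the cohort 4 eligibility criteria do not require it

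*Combined protocol and SAP*

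**What the plan says.** Section 9.0 (Ethics and Protection of Human Subjects) describes the study as minimal risk, depending on age, and gives one step taken to reduce that risk: "We have sought to minimize the risk by obtaining approval from their treating oncologist prior to participation". It names no cohort.

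Section 4.3 (Inclusion/Exclusion Criteria) has three inclusion lists. The cohort 1-3 list contains "Obtained approval from oncologists for the participant to be involved in the physical activity based support group". The other two lists are headed "Primary inclusion criteria for Cohort 4 due to grant restrictions will include" and "Inclusion criteria for Cohort 4 due to pandemic (e.g., COVID-19) restrictions will include". Neither mentions an oncologist. For exclusions, the section says: "Ineligibility criteria for Cohort 4 will include all criteria listed above". It then adds one exclusion, for lack of an internet-connected device.

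Section 4.2 (Participant Recruitment) has oncologists refer patients and says: "The team will not approach patients until they provided the permission for the team to approach". The same section also provides for registry letters and local support groups, and says: "Newspaper advertisement and flyers will also be used as additional recruitment tools". It sets the cohort 4 arms at "10 in the intervention group and 10 in the control group".

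**The concern.** Section 4.3 makes a person eligible when she meets every inclusion criterion and no exclusion. A cohort 4 candidate can do so without any clinician having agreed that she may exercise. The ethics section nevertheless reports that agreement as the way risk is kept low, so a reader or an ethics board would believe that a control is in place that the criteria do not require.

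This bears on patient safety, to a moderate degree. Cohort 4 is limited to ages 55 to 79. None of its criteria is a medical clearance: the only physical requirement is to be able to move the limbs and walk, and the exclusions are pregnancy, dementia, already being active, being in another activity programme, and having no device. The ethics section itself warns that vigorous activity may cause serious injury, and the Data and Safety Monitoring Plan includes cardiac events among the events it anticipates.

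One other protection is also weaker for this cohort. Section 5.1 places function testing at UTMB sites with nursing staff nearby. Table 4 moves the SPPB, the 2-minute step test and the Timed Up and Go to video conference under pandemic restrictions, for both arms.

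**Working it through.** The plan gives no figure to reproduce. The check compares texts and then counts people.

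**Step 1. Where approval is required (section 4.3).**

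| List | Lines | Lines requiring oncologist approval |
|---|---|---|
| Inclusion, cohorts 1-3 | 8 | 1 |
| Inclusion, cohort 4, grant restrictions | 7 | 0 |
| Inclusion, cohort 4, pandemic restrictions | 6 | 0 |
| Exclusions applying to cohort 4 (4 general + 1 added) | 5 | 0 |

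For cohort 4 this is 0 of 7 + 6 + 5 = 18 lines. The two inclusion lists overlap, so 18 is only a tally of the lines searched.

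**Step 2. Whether approval carries over.** The only sentence that extends earlier criteria to cohort 4 concerns the ineligibility criteria. None of those involves an oncologist, so the cohort 1-3 approval line does not reach cohort 4.

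**Step 3. Whether recruitment supplies it.** The section 4.2 safeguard is a permission to make contact, and it is unclear whether the oncologist or the patient gives it. Oncologists outside the protocol receive a flyer for referral, and interested patients then contact the researchers themselves. Registry letters, newspaper advertisements and general flyers need not pass through an oncologist at all. On no route does the text require clearance to exercise.

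**Step 4. Whether another section requires it.** Neither section 5.1 nor the Data and Safety Monitoring Plan asks for oncologist approval for cohort 4.

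**Step 5. How many people this concerns.** Planned randomisation is 60 in cohorts 1-3 and 20 in cohort 4, in total 80 (section 4.2).

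- Covered by a written approval criterion: 60/80 = 75%.
- Not covered: 20/80 = 25%. This is a ceiling.
- Of those, in the arm that does web-based games and grip exercise: 10/80 = 12.5%, which is 10/20 = 50% of cohort 4.
- The other 10 receive calls and a tracker, but they also take the physical function tests.

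The number who would actually enter without approval lies between 0 and 20. It depends on the screening script and on how many are referred by an oncologist who has in effect agreed.

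**The case against.** The strongest reply is that the documents show two sections that disagree, not a plan that admits cohort 4 without approval. The ethics sentence is itself part of the plan and, read literally, covers everyone. Staff determine eligibility from the screening script (Appendix A), which was not among the documents reviewed and may ask for approval. The sentence may also be left over from cohorts 1-3: it looks back on what was done, and the next paragraph still gives controls a basic pedometer, whereas cohort 4 controls receive a wearable tracker. The cohort 4 lists were written separately and differ in other ways, so approval may have been dropped on purpose.

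It can also be said that other protections remain. Section 5.1 provides for difficulty that rises slowly, warm-up and cool-down, an occupational therapist, and weekly questions on how participants feel. The principal investigator reviews screening and session logs. Section 6.0 discontinues a participant whose medical condition makes continuing unwise in the opinion of the principal investigator or treating staff. Table 4 drops the fitness-test components that could not be adapted safely. Activity starts with two minutes of walking.

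Much of this stands, and it limits the severity. Approval may well be obtained in practice, and no harm has been quantified: the 0 to 20 range is a head count. The move to video testing is a related but separate weakness, since an oncologist's approval would not restore on-site supervision. But none of these points removes the mismatch. If the sentence is out of date, it still claims a control that the cohort 4 criteria do not contain. The section 6.0 rule acts only after entry. The remaining protections manage exercise once it has begun; none is a clinician's judgement that this person may start.

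**Conclusion.** The point holds: the plan is wrong as written, at moderate severity. The written criteria do not require for cohort 4 a safeguard that the ethics section says is in place. The ceiling is 20 of 80 planned participants (25%), of whom 10 (12.5% of 80) would do the exercise programme.

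Confidence is high for the mismatch, which follows from the text alone. The practical consequence is less certain. It rests on the assumption that the screening script does not itself require approval, and on how many cohort 4 participants come by routes that do not involve an oncologist. The documents settle neither.

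**What to change.** **Default.** Add an approval line, reworded for the web-based programme, to both cohort 4 inclusion lists and to the screening script. For example: *The treating oncologist has agreed that the participant may take part in the web-based active video game and grip exercise programme and in the physical function tests.* Obtain it before the first physical function test, and for both arms, because allocation is not yet known then and controls take the tests too.

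**Alternative**, only if the investigators and the IRB deliberately dropped approval for cohort 4: limit the ethics sentence to cohorts 1-3 and name the protections relied on for cohort 4.

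**Cost.** The default changes one line in two lists and in the script. It needs one approval request per candidate: 20 if asked only of those who go on to be randomised, up to 80 if asked of everyone recruited for cohort 4 (section 4.2), with some enrolment delay. The alternative is a wording change only. Neither affects an endpoint, the sample size or the analysis.

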## 9.0 Data and Safety Monitoring Plan

The PI [name] will make up the study safety team and oversee all participant safety and data monitoring. The PI is responsible for monitoring procedures during conduct of the study for each participant including: eligibility, enrollment, data collection, evaluation of study outcomes, problems with informed consent, and participant safety and well-being. [name] will be the point of contact for all study-related personnel who come into contact with and monitoring the safety of research participants. An Occupational Therapist will oversee grip strengthening exercises, home exercise worksheets, and will be responsible for modification of activity. All study personnel will be responsible for monitoring for any potential adverse events or negative reactions. The coordinator will be the point of contact for study participants and will assess for all safety concerns, make necessary inquiries with participants, and document all potential adverse events.

The plan for monitoring will include:

1. Regular review of screening call logs by PI
2. Regular review of group session logs by PI
3. Regular review of collected data performed by PI and investigator team
4. Annual review by PI and UTMB IRB

Review of screening call logs on a regular basis will ensure that any values indicating ineligibility and/or unsafe practices are flagged. Flagged participants may be excused from the study or instructed on safer practices as needed. Group session logs completed by the facilitator and project staff will also be reviewed by the PI. Any indication of an adverse event or unsafe practices will also be flagged. In the case of adverse events, stand protocol for reported adverse events will be used. Study data will be reviewed by the PI and investigator team. Again, the team will identify any values indicating unsafe practices or potential adverse events that may not have been reported by participants. Finally, the UTMB IRB will review study progress yearly.

As this is a low-risk study, we do not anticipate any serious adverse events or safety concerns. Thus, we will not perform full statistical analysis during these periodic reviews. Though we anticipate possible differences in health outcomes, for the study to be rigorous, we must continue to measure all planned variables at each planned time point. The reviews will focus on indicators of safety for participants, such as large decreases in quality of life or strength, or large weight gains. We will create a list of a priori criteria for quantifying clinically significant change based on adverse events information published by the NCI. (For example, a weight gain of 5-10% would be considered a mild adverse event.)

We will not convene an external Data Safety and Monitoring Board.

Anticipated non-serious adverse events include musculoskeletal pain or mild injuries, other non-serious injuries (e.g., bruises), skin irritation, minor discomfort, cardiac events, fatigue, weight gain, and possible loss of confidentiality. If an anticipated adverse event occurs, the PI will immediately confer regarding each event. The attribution and impact of each event on the

overall project's risk/benefit ratio will then be determined.

All unanticipated, serious, fatal, and/or life-threatening adverse events will be immediately reported to the UTMB IRB within 24 hours of occurrence. The IRB and PI are responsible for determining if modifications are needed to the consent form and/or protocol based on the event. If a determination is made that participants are exposed to unacceptably high risk in comparison to benefit, the study will be suspended until proper modifications are made for participant safety. Aggregate reports of adverse events will be prepared in consultation with the regulatory key resource of the Institute for Translational Sciences at UTMB and forwarded to the IRB for review.

**9.1 Plan for data management.** For self-report and feasibility data, the PI is responsible for collection and storage of data initially on electronic questionnaires and saved assessment information from the paper format, then transferred to a computer database located on a secure UTMB server. Questionnaire data will not be personally identifiable. All questionnaires will use ID numbers for identification purposes, and the correspondence of ID numbers to names will be kept in a password-protected file on a password-protected, secure server. Databases will use ID numbers for identification of data and will also be stored on the secure, password-protected server. The data collected by the game consoles will not be directly linked to the participants because pseudonyms were provided for each participant. Data saved by the game consoles will be moved and erased from the console prior to further use of the console or provision to another participant.

**9.2 Plan for adverse event reporting.** The PI will also hold responsibility for monitoring and reporting adverse events of any kind. We do not anticipate severe adverse events, though mild and moderate events are possible. The scale to be used is the UTMB Clinical Research Center Adverse Event Grading Scale (Table 5). Examples of each level of adverse event on the scale are provided below.

- **Mild** events include discomfort without disruption of daily activities. No therapy or only symptomatic therapy is required. This level is equivalent to NCI Common Terminology Criteria for Adverse Events version 4.03 Grade 1 adverse events (mild; asymptomatic or mild symptoms; intervention not indicated).
- **Moderate** events include discomfort sufficient to modify daily normal activity. Specific therapy is required. Laboratory test alterations indicate injury without long-term risk. This level is equivalent to NCI Grade 2 (moderate; minimal, local or noninvasive intervention indicated; limiting age-appropriate activities of daily living).
- **Severe** events include incapacity, inability to work, inability to perform normal daily activity, hospitalization required, prolonged emergency treatment required, life-threatening events, laboratory tests indicating a serious health threat or permanent injury, and death. This level is equivalent to NCI Grades 3 (severe/medically significant but not immediately life-threatening), 4 (life-threatening, urgent intervention indicated), and 5 (death).

